6.3. Lifestyle Restrictions

6.3.1. Meals and Dietary Restrictions

Participants should avoid consumption of red wine, Seville oranges, grapefruit or grapefruit juice (and/or pomelos, exotic citrus fruits, grapefruit hybrids or fruit juices) from 5 days before the first dose of study medication, until follow-up.

Participants should refrain from eating poppy seed-containing food (e.g., poppy cake) at least 3 days before admission as this can falsify the urine drug screen. A positive illicit drug result will lead to exclusion from the remainder of the study.

• Water is allowed ad libitum throughout the study.

- While in residence in the clinical research unit (admission through discharge), participants will be restricted to food and beverage that is site-provided at specific times. Participants are expected to complete all meals and snacks (100%) within 25 minutes (Parts 1A and Part 1B). Non-compliance will be recorded.
- Participants will be fed a "normal" standardized diet consisting of an average between 3400 to 4000 kcal for each full day in residence (with the exception of Part 1B dosing days where dosing is conducted under fasted conditions). A 5% variance in calories is allowed. The macronutrient distributions and caloric criteria are within the recommendations in the *Dietary Guidelines for Americans*, 2010.

• Part 1A and Part 2

- Standardized meals will be provided to participants in Part 1A starting with Day 1 through discharge from the clinical research unit.
- Standardized meals and snacks should be completed within 25 minutes. Participants will be expected to complete all meals and snacks (100%). Non-compliance on Day 1 will be recorded in increments of 25% (e.g., 0%, 1-25%, 26-50%, 51-75% or 76-100% meal or snack completed).
- Participants will undergo at least a 10-hour overnight fast then will be provided a meal 30 minutes before dosing and will be expected to complete the meal within 25 minutes. Lunch will be provided approximately 4 hours after morning dosing and dinner will be provided approximately 9 hours after morning dosing. On Day 1, all participants will receive identical meals at breakfast, lunch, dinner and snack. On non-dosing days, meals will be served per the standard times at the clinical research unit.

• Part 1B (tablet, fasted):

• Participants will undergo at least a 10-hour overnight fast prior to Part 1B GSK2838232 tablet dosing. On the day of dosing, participants will continue fasting after dosing (no breakfast). Lunch will be provided approximately 4 hours after morning dosing and dinner will be provided approximately 9 hours after morning dosing. On Day 1, all participants will receive identical meals at lunch, dinner and snack. On non-dosing days, meals will be served per the standard times at the clinical research unit.

6.3.2. Caffeine, Alcohol, and Tobacco

- All enrolled participants will abstain from ingesting caffeine- or xanthine-containing products (e.g., coffee, tea, cola drinks and chocolate) for 48 hours before the start of dosing until collection of the final PK sample during each session.
- All enrolled participants will abstain from red wine for 5 days and other alcohol
 for 24 hours before the start of dosing until collection of the final PK sample
 during each session.

- Participants who currently use or have used tobacco products within 6 months of Screening will not be enrolled.
- Participants must refrain from all illicit drugs throughout the study (from
 Screening until discharge from the study). Drug screening will occur as indicated
 in the Schedule of Assessments (Table 2 and Table 3) for each Part of the study.
 Participants should refrain from eating poppy seed-containing food (e.g., poppy
 cake) at least 3 days before admission as this can falsify the urine drug screen. A
 positive illicit drug result will lead to exclusion from the remainder of the study.

6.3.3. Activity

• Participants will abstain from strenuous exercise for 1 week before Admission and during the course of the study and refrain from increasing their activity above that which they normally perform. Participants may participate in light recreational activities during studies (e.g., watch television, read).

6.4. Screen Failures

Screen failures are defined as participants who consent to participate in the clinical study but are not subsequently randomized. A minimal set of screen failure information is required to ensure transparent reporting of screen failure participants to meet the Consolidated Standards of Reporting Trials (CONSORT) publishing requirements and to respond to queries from regulatory authorities. Minimal information includes demography, screen failure details, eligibility criteria, and any SAEs.

Individuals who do not meet the criteria for participation in this study (screen failure) may be rescreened at the discretion of the PI. Rescreened participants should be assigned the same participant number as for the initial screening.

7. TREATMENTS

The term 'study treatment' is used throughout the protocol to describe GSK2838232, RTV or the combination of the products received by the participant as per the protocol design.

GSK2838232 will be supplied by GSK as prefilled capsules or tablets in bulk for dispensing to participants at the site according to the treatment code.

Ritonavir – commercially available; will be purchased/supplied either by PAREXEL or GSK.

7.1. Treatments Administered

Details of the study treatment are provided in Table 5 below.

 Table 5
 Investigational Product and Other Study Treatment

Study Treatment Name:	GSK2838232	NORVIR (ritonavir, RTV)	Placebo (Part 2 only)
Dosage formulation:	Tablets or Capsule	Tablets	*Tablet (non-matching) for the GSK2838232 tablet formulation)
Unit dose strength(s)/Dosage level(s):	200 mg: Capsules: 4 x 50 mg Tablets: 2 x 100 mg	100 mg	Not applicable
Route of Administration	Oral	Oral	Oral
Dosing instructions:	Part 1A: To be taken with water and a meal (fed conditions) Part 1B: To be taken with water after a fast (fasted conditions) Part 2: To be taken with water and a meal once daily for 11 consecutive days	Part 1A: To be taken with water and a meal (fed conditions) Part 1B: To be taken with water after a fast (fasted conditions)	Part 2: To be taken with water and a meal once daily for 11 consecutive days
Packaging and Labeling	GSK2838232 will be supplied by GSK as prefilled capsules or tablets in bulk for dispensing to participants at the site according to the treatment code.		Placebo for GSK2838232 tablets will be provided, although are non-matching as tablets
Manufacturer/Source of procurement	GSK	Procured by PAREXEL	GSK
Physical Form	Pink unmarked capsule White to slightly colored tablet.	White film-coated ovaloid tablets	White to slightly colored tablet.

*The placebo (tablet) supplied will not be identical to GSK2838232 and as such will be administered by site staff via an opaque card/paper tube to facilitate the single blind (i.e., the participant will be blinded as to their treatment).

CONFIDENTIAL

The unblinded pharmacist or qualified designee will prepare GSK2838232 and placebo according to a pre-generated schedule of randomized treatment assignments.

7.1.1. Medical Devices

• Not applicable.

7.2. Dose Modification

Not applicable.

7.3. Method of Treatment Assignment

Participants will be assigned to study treatment in accordance with the computer generated randomization schedule generated by PAREXEL, using SAS version 9.3 or higher. A separate randomization schedule will be generated for each part of the study. At Screening, potential study participants will be assigned a screening number. Participants will be randomized before the first dose of Study Drug in Part 1A (GSK2838232 tablet or capsule, with RTV) or Part 2 (GSK2838232 tablet or placebo tablet, without RTV) after all screening assessments have been completed and after the Investigator has verified that they are eligible per study inclusion/exclusion criteria. No participant may begin treatment before randomization and assignment of a unique participant identification number.

Each participant scheduled to receive study treatment will receive a participant number when randomized. The randomization number will determine the allocation of treatment sequences (ABC or BAC) for Part 1, and of treatment (GSK2838232 without RTV or placebo) for Part 2. Allocation to treatment for Part 1A or Part 1B (with Part 2 being fixed) will be according to a predetermined random order.

7.4. Blinding

Part 1 of the study will be open label and thus not be blinded.

Part 2 of the study will be single blinded because of the unavailability of matching placebo tablets. Certain site personnel preparing the treatment for administration will know what the treatment is but will administer the tablet or tablet placebo via an opaque tube/envelope to the participants. The PI and the participants will be completely blinded to specific participant treatment assignment.

When possible, GSK/ contract research organization (CRO) personnel will not have access to participant-specific treatment assignment so as to not potentially introduce bias in discussions with the study center.

The Investigator or treating physician may unblind a participant's treatment (Part 2 single blind) assignment **only in the case of an emergency** when knowledge of the study treatment is essential for the appropriate clinical management or welfare of the participant. Whenever possible, the Investigator must first discuss options with the GSK Medical Monitor or appropriate GSK study personnel **before** unblinding the participant's treatment assignment. If this is impractical, the Investigator must notify GSK as soon as possible, but without revealing the treatment assignment of the unblinded participant, unless that information is important for the safety of participants currently in the study. The date and reason for the unblinding must be recorded in the appropriate data collection tool.

A participant will be withdrawn if the participant's treatment code is unblinded by the Investigator or treating physician. The primary reason for discontinuation (the event or condition which led to the unblinding) will be recorded in the data collection tool.

GSK's Global Clinical Safety and Pharmacovigilance (GCSP) staff may unblind the treatment assignment for any participant with an SAE. If the SAE requires that an expedited regulatory report be sent to one or more regulatory agencies, a copy of the report, identifying the participant's treatment assignment, may be sent to Investigators in accordance with local regulations and/or GSK policy.

7.5. Preparation/Handling/Storage/Accountability

A description of the methods and materials required for preparation of GSK2838232, RTV or placebo will be detailed in a Technical Agreement. The formulations will be extemporaneously prepared as per instructions that will be reviewed and approved by GSK before use.

- 1. The Investigator or designee must confirm appropriate temperature conditions have been maintained during transit for all study treatment received and any discrepancies are reported and resolved before use of the study treatment.
- 2. Only participants enrolled in the study may receive study treatment and only authorized site staff may supply or administer study treatment. All study treatments must be stored in a secure, environmentally controlled, and monitored (manual or automated) area in accordance with the labeled storage conditions with access limited to the Investigator and authorized site staff.
- 3. The Investigator, institution, or the head of the medical institution (where applicable) is responsible for study treatment accountability, reconciliation, and record maintenance (i.e., receipt, reconciliation, and final disposition records).
- 4. Further guidance and information for the final disposition of unused study treatment are provided in the Study Reference Manual.
- 5. Under normal conditions of handling and administration, study treatment is not expected to pose significant safety risks to site staff.
- 6. A Material Safety Data Sheet (MSDS)/equivalent document describing occupational hazards and recommended handling precautions either will be provided to the

Investigator, where this is required by local laws, or is available upon request from GSK.

7.6. Treatment Compliance

- When the individual dose for a participant is prepared from a bulk supply, the preparation of the dose will be confirmed by a second member of the study site staff.
- When participants are dosed at the site, they will receive study treatment directly from the Investigator or designee, under medical supervision. The date and time of each dose administered in the clinic will be recorded in the source documents. The dose of study treatment and study participant identification will be confirmed at the time of dosing by a member of the study site staff other than the person administering the study treatment. Study site personnel will examine each participant's mouth to ensure that the study treatment was ingested.

7.7. Concomitant Therapy

Any medication or vaccine (including over-the-counter or prescription medicines, vitamins, and/or herbal supplements) that the participant is receiving at the time of enrollment or receives during the study must be recorded along with:

- reason for use,
- dates of administration including start and end dates,
- dosage information including dose and frequency.

The Medical Monitor should be contacted if there are any questions regarding concomitant or prior therapy.

Participants must abstain from taking prescription or nonprescription drugs (including vitamins and dietary or herbal supplements) within 7 days (or 14 days if the drug is a potential enzyme inducer) or 5 half-lives (whichever is longer) before the start of study treatment until completion of the follow-up visit, unless, in the opinion of the Investigator and sponsor, the medication will not interfere with the study.

Acetaminophen, at doses of ≤ 2 g/day is permitted for use any time during the study. Other concomitant medication may be considered on a case by case basis by the Investigator in consultation with the Medical Monitor.

7.8. Treatment after the End of the Study

Participants will not receive any additional treatment from GSK after completion of the study because only healthy participants are eligible for study participation.

[figure not shown]
8. DISCONTINUATION CRITERIA

8.1. Discontinuation of Study Treatment

8.1.1. Liver Chemistry Stopping Criteria

Study treatment will be discontinued **for a participant** if liver chemistry stopping criteria are met:

Phase I Liver Chemistry Stopping Criteria – Liver Stopping Event Algorithm

Liver Safety Required Actions and Follow up Assessments Section can be found in Section 12.3, Appendix 3.

Liver chemistry stopping and increased monitoring criteria have been designed to assure participant safety and evaluate liver event etiology (in alignment with the Food and Drug Administration [FDA] premarketing clinical liver safety guidance). These protocol guidelines are in alignment with FDA premarketing clinical liver safety guidance:

http://www.fda.gov/downloads/Drugs/GuidanceComplianceRegulatoryInformation/Guidances/UCM174090.pdf.

Discontinuation of study treatment for abnormal liver tests should be considered by the Investigator when a participant meets one of the conditions outlined in the algorithm above or if the Investigator believes that it is in the best interest of the participant.

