9. STUDY ASSESSMENTS AND PROCEDURES

Each participant will have adequate time to provide informed consent of his or her own free will and before conducting any study procedures according to the International Conference on Harmonization (ICH) and Code of Federal Regulations (CFR) guidelines. Each participant will be provided a copy of the signed informed consent document (ICF) before the initiation of any study procedures.

After a participant has provided written informed consent and within 30 days of the first dose of study treatment, the Investigator or other study personnel will determine if the participant is eligible for enrolment in the study. This will be done by reviewing the inclusion and exclusion criteria and completing all of the screening assessments outlined in the Schedule of assessments Tables (Table 2 and Table 3). Screening assessments may be carried out over more than 1 day provided that all required assessments are completed within 30 days before the first administration of study treatment.

Protocol waivers or exemptions are not allowed with the exception of immediate safety concerns. Therefore, adherence to the study design requirements, including those specified in the Schedule of Assessments Tables (Table 2 and Table 3), are essential and required for study conduct.

Whenever vital signs, 12-lead ECGs and blood draws are scheduled for the same nominal time, the assessments should occur in the following order:

- 1. 12-lead ECG.
- 2. Vital signs.
- 3. Blood draws.

Note: The timing of the assessments should allow the blood draw to occur at the exact nominal time. In the event that the timing for a scheduled assessment conflicts with an

assessment that has to be repeated, the scheduled assessment will be performed on time/as scheduled and the repeat assessments will be conducted when feasible.

The timing and number of planned study assessments, including: safety and PK assessments may be altered during the course of the study based on newly available data (e.g., to obtain data closer to the time of peak plasma concentrations) to ensure appropriate monitoring.

The Institutional Review Board (IRB) will be informed of any safety issues that require alteration of the safety monitoring scheme or amendment of the Informed Consent Form.

The timing of planned study assessments is listed in the Schedule of Assessments Tables (Table 2 and Table 3).

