12.3. Appendix 3: Liver Safety: Required Actions and Follow-up Assessments

Phase 1 Liver chemistry stopping criteria have been designed to assure participant safety and to evaluate liver event etiology (in alignment with the FDA premarketing clinical liver safety guidance).

http://www.fda.gov/downloads/Drugs/GuidanceComplianceRegulatoryInformation/Guidances/UCM174090.pdf.

Phase I liver chemistry stopping criteria and required follow up assessments

Liver Chemistry Stopping Criteria				
bilirubin) or INR > 1.5, Re	ALT \geq 3 x ULN AND bilirubin ^{1,2} \geq 2 x ULN (> 35% direct bilirubin) or INR > 1.5, Report as an SAE. See additional Actions and Follow Up Assessments listed below			
Required Actions and Follow up Assessme	nts			
Actions	Follow Up Assessments			
 Report the event to GSK within 24 hours Complete the liver event CRF, and complete an SAE data collection tool if the event also meets the criteria for an SAE² Perform liver event follow up assessments Monitor the participant until liver chemistries resolve, stabilise, or return to within baseline (see MONITORING below) Viral hepatitis serology³ Obtain INR and recheck with liver chemistry assessment un transaminases values show do trend Obtain blood sample for pharmacokinetic (PK) analysi and lactate dehydrogenase (LI Fractionate bilirubin, if total be ≥ 2 x ULN 				
 MONITORING: If ALT ≥ 3 x ULN AND bilirubin ≥ 2 x ULN or INR > 1.5 Repeat liver chemistries (include ALT, AST, alkaline phosphatase, bilirubin) 	 Obtain complete blood count with differential to assess eosinophilia Record the appearance or worsening of clinical symptoms of liver injury, or hypersensitivity, on the AE report form 			

Liver Chemistry Stopping Criteria

assessments within 24 hours

- Monitor participants twice weekly until liver chemistries resolve, stabilise or return to within baseline
- A specialist or hepatology consultation is recommended

If ALT \geq 3 x ULN AND bilirubin \leq 2 x ULN and INR \leq 1.5:

- Repeat liver chemistries (include ALT, AST, alkaline phosphatase, bilirubin) and perform liver event follow up assessments within 24 to 72 hours
- Monitor participants weekly until liver chemistries resolve, stabilize or return to within baseline

- Record use of concomitant medications on the concomitant medications report form including acetaminophen, herbal remedies, other over the counter medications.
- Record alcohol use on the liver event alcohol intake case report form

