If ALT \geq 3 x ULN AND bilirubin \geq 2 x ULN or INR \geq 1.5:

- Anti-nuclear antibody, anti-smooth muscle antibody, Type 1 anti-liver kidney microsomal antibodies, and quantitative total immunoglobulin G (IgG) or gamma globulins.
- Serum acetaminophen adduct high performance liquid chromatography (HPLC) assay (quantifies potential acetaminophen contribution to liver injury in participants with definite or likely acetaminophen use in the preceding week [James, 2009].
- Liver imaging (ultrasound, magnetic resonance, or computerised tomography) and /or liver biopsy to evaluate liver disease; complete Liver Imaging and/or Liver Biopsy CRF forms.
- 1. Serum bilirubin fractionation should be performed if testing is available. If serum bilirubin fractionation is not immediately available, discontinue study treatment for that participant if $ALT \ge 3 \times ULN$ and bilirubin $\ge 2 \times ULN$. Additionally, if serum bilirubin fractionation testing is unavailable, record presence of detectable urinary bilirubin on dipstick, indicating direct bilirubin elevations and suggesting liver injury.
- 2. All events of ALT ≥ 3 x ULN and bilirubin ≥ 2 x ULN (> 35% direct bilirubin) or ALT ≥ 3 x ULN and INR > 1.5, if INR measured, which may indicate severe liver injury (possible 'Hy's Law'), must be reported as an SAE (excluding studies of hepatic impairment or cirrhosis); INR measurement is not required and the threshold value stated will not apply to participants receiving anticoagulants.

3. Includes: Hepatitis A IgM antibody; Hepatitis B surface antigen and Hepatitis B Core Antibody (IgM); Hepatitis C RNA; Cytomegalovirus IgM antibody; Epstein-Barr viral capsid antigen IgM antibody (or if unavailable, obtain heterophile antibody or monospot testing); Hepatitis E IgM antibody.

12.4. Appendix 4: Division of AIDS Table For Grading The Severity of Adult and Pediatric Adverse Events

The DAIDS Table [Division if AIDS (DAIDS) Table (NIH), 2014] will be used to grade the severity of an AE that is not specifically identified in the grading table. In addition, all deaths related to an AE are to be classified as grade 5.

	Grade 1 Mild	Grade 2 Moderate		Grade 4 Potentially Life Threatening
	Mild symptoms		J 1	Potentially life-
adverse event	_	J 1		threatening
NOT	minimal	causing greater	perform usual	symptoms causing
identified	interference	than minimal	social & functional	inability to perform

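### Section 8.1.1 of the protocol gives a mandatory and a discretionary instruction for the same liver stopping criteria; one sentence needs rewording

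*Protocol*

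**What the plan says.** Protocol Section 8.1.1 is headed as a section on liver chemistry stopping criteria. It begins: "Study treatment will be discontinued" for a participant who meets those criteria. It then names a "Liver Stopping Event Algorithm", refers the reader to Appendix 3 (Section 12.3) for required actions, and adds that "Liver chemistry stopping and increased monitoring criteria have been designed to assure participant safety".

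The section ends with a second statement about stopping: "Discontinuation of study treatment for abnormal liver tests should be considered by the Investigator when a participant meets one of the conditions" set out in the algorithm above. As an alternative ground it adds the investigator's own view of the participant's best interest.

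Appendix 3 lists what follows a liver event. The list includes "Report the event to GSK within 24 hours", and for the less severe tier a requirement to repeat the chemistries "and perform liver event follow up assessments within 24 to 72 hours". Footnote 1 gives a direct order for one situation: "If serum bilirubin fractionation is not immediately available, discontinue study treatment for that participant if" ALT is at least 3 x ULN and bilirubin at least 2 x ULN.

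**The concern.** A stopping rule is useful because it removes the decision at the moment it is triggered. Here the first sentence removes the decision and the last one gives it back, for conditions that include the stopping criteria themselves. An investigator who relied on the closing sentence could consider stopping, decide against it, and believe that the protocol had been followed.

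The participants are healthy and expect no benefit from treatment (Section 3.3.2). Section 3.3.3 relies on liver stopping criteria as one of three measures against liver risk, alongside exclusion of people with hepatic or biliary abnormalities and monitoring of liver enzymes. Dose modification (7.2) and temporary discontinuation (8.1.3) are both marked not applicable, so the choice after an event is to stop or to continue unchanged.

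The stake should not be overstated. Section 3.3.3 describes the liver findings in the 9-month dog study as mild, reversible and open to monitoring, and as seen only after prolonged exposure above the average expected at this study's highest dose. Dosing in Part 2 lasts 11 days. What is at stake is the clarity of a safety rule, not a demonstrated hazard.

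**Working it through.** No arithmetic applies. The check is a comparison of texts.

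| Place in protocol | What it says about stopping | Force |
|---|---|---|
| 8.1.1, opening | "Study treatment will be discontinued" if the stopping criteria are met | Mandatory |
| 8.1.1, closing, first ground | Discontinuation is to be considered when a condition in the algorithm is met | Discretionary |
| 8.1.1, closing, second ground | Discontinuation is to be considered if it serves the participant's best interest | Discretionary, and properly so |
| 3.3.3 | Liver stopping criteria will be put into effect | Favours mandatory |
| 9 | "Protocol waivers or exemptions are not allowed with the exception of immediate safety concerns" | Favours mandatory |
| Appendix 3, footnote 1 | Stop at the stated ALT and bilirubin levels when bilirubin cannot be fractionated at once | Mandatory, for one situation |

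**Step 1: do the two sentences of 8.1.1 cover the same conditions?** The opening covers the stopping criteria. The closing covers the conditions in the algorithm above it, and the only algorithm named in the section is the "Liver Stopping Event Algorithm". By its title, the stopping criteria are among its conditions. The two sentences therefore overlap on the stopping criteria.

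**Step 2: does the answer depend on the algorithm figure?** The figure is not reproduced in the text available here, so take the possibilities in turn.

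- If it holds only stopping criteria, the two sentences give different instructions for an identical set.
- If it also holds increased-monitoring conditions, the closing sentence applies consideration to all of them, stopping criteria included.
- If its boxes say to stop, the figure supports the opening sentence, but the closing sentence still asks only for consideration when those boxes are reached.

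The overlap remains in each case.

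**Step 3: can the closing sentence be read as only adding discretion?** Its second ground does exactly that. Its first ground does not: it takes the algorithm's conditions and makes them a prompt for consideration.

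**Step 4: does other text settle which sentence governs?** All of it leans towards mandatory stopping, but none of it ranks the two sentences. The no-waivers clause requires adherence to the protocol, and both sentences are protocol text. Footnote 1 is limited to the case where fractionation is not immediately available. Section 3.3.3 promises stopping criteria without stating their force.

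**Step 5: compare the neighbouring rule.** The QTc rule in 8.1.2 says that a participant who meets the criterion will be withdrawn from study treatment, and nothing later in that section softens it. The liver rule could be written in the same way.

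**The case against.** The strongest reply is that the section, read as a whole, is already mandatory. The heading speaks of stopping criteria, the opening sentence is unconditional, and the closing sentence does not revoke it. Footnote 1 orders a stop when bilirubin has not been fractionated, which is the less certain case, so it would be odd if the confirmed case were optional. Continuing to dose after a stopping event would breach the opening sentence and count as a protocol deviation. Much of this stands. It is the better reading, and many investigators would stop in any case. It does not remove the difficulty that a reader must discount one sentence of a safety rule to reach it.

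Three stronger readings are tempting, and the documents do not support them.

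- *The plan fails to separate stopping criteria from increased-monitoring conditions.* The prose of 8.1.1 names both together, but the natural place to separate them is the algorithm, and a figure that cannot be seen here cannot be counted as missing from the plan.
- *The size can be given as doses received after an event*, for example 9 or 10 of the 11 Part 2 doses following a Day 2 result. Such counts describe an investigator who sets aside the opening sentence and keeps dosing through the reporting and repeat testing that Appendix 3 requires. They measure a hypothetical breach, and the documents give no liver event rate to weight them.
- *Appendix 3 contains no instruction to stop outside footnote 1.* That table may be broken in extraction, so nothing should rest on it.

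**Conclusion.** The concern holds as an inconsistency of wording. Section 8.1.1 attaches two strengths of instruction to the same liver stopping criteria, and no other visible text says which prevails, although all of it favours mandatory stopping. The closing sentence leaves room to treat a met criterion as a matter of judgement.

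Severity is low. No estimate, confidence interval, sample size or analysis population is affected, and there is no number to attach to the point. The conclusion rests only on the visible sentences of 8.1.1 and on the algorithm's title. It does not depend on the content of the figure, on an assumed event rate, or on the animal liver findings implying appreciable risk at these exposures. The point is worth acting on because the rule protects healthy participants and is easily made unambiguous.

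**What to change.** Keep the opening sentence of 8.1.1 as the rule for any participant who meets a liver stopping criterion. Replace the closing sentence with one limited to the remaining cases, along these lines: *For abnormal liver tests that do not meet a stopping criterion, the Investigator should consider discontinuation where this is in the participant's best interest.*

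The cost is one sentence in the protocol. Thresholds, visit schedule, Appendix 3 actions, sample size and analyses stay as they are, and the SAP's liver displays need no change.
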